7.4 NUMBER OF SUBJECTS

Two-hundred and fifty (250) subjects will be implanted at up to twenty-five (25) centers in Europe. The enrolment period completion is anticipated to be two (2) years.

8.0 STUDY POPULATION

8.1 SUBJECT INCLUSION CRITERIA

A subject who meets ***all of the following criteria*** potentially ***may be included*** in the study:

1. Subject is \geq 18 years old
2. Presence of severe MR as read on a transthoracic echocardiographic study
3. Mitral leaflet coaptation surface is sufficient to reduce mitral regurgitation without undue leaflet tension (approximate leaflet to gap ratio of 2:1) based on the judgment of the patient eligibility committee and the operating surgeon
4. Degenerative mitral valve disease with mid-segment P2 prolapse
5. Patient is able to sign informed consent and able to return for follow-up and is capable of participating in all testing associated with this clinical investigation

8.2 SUBJECT EXCLUSION CRITERIA

A subject who meets ***any of the following criteria will not be included*** in the study:

1. Patient is of the age where further growth is expected
2. Active endocarditis
3. Left ventricular or left atrial appendage thrombus
4. Severe mitral annular and/or leaflet calcification
5. Cannot tolerate procedural anticoagulation or post-procedure antiplatelet regimen
6. Mitral stenosis
7. Functional Mitral Valve disease
8. Previous mitral valve replacement surgery
9. Fragile or thinning apex
10. Contraindications to transesophageal echocardiography (atlantoaxial disease, severe generalized cervical arthritis, upper gastrointestinal bleeding, significant dysphagia and odynophagia, has received extensive radiation to the mediastinum).
11. Patient is pregnant or lactating

8.3 SCREENING AND ENROLMENT

All subjects who are clinically suitable for treatment with the HARPOON System, and who meet the study inclusion/exclusion criteria will be approached for inclusion in the study. (Subjects who do not wish to participate in the study may be treated with the HARPOON System outside of the study.) Subjects who agree to participate will sign an Ethics Committee (EC)-approved study informed consent and will be considered part of the enrolled population.

8.4 SUBJECT AND STUDY DURATION

The total enrolment period for this study is estimated to be two years, with an estimated start date in Q4 2019 and estimated completion in Q4 2021. Follow-up for implanted subjects is five years, therefore the entire study duration is seven years, with an estimated completion in Q1 2027.

9.0 STUDY PROCEDURES AND SCHEDULE OF ASSESSMENTS

9.1 SUBJECT SCREENING AND INFORMED CONSENT

All subjects who are clinically suitable for treatment with the HARPOON System and meet study eligibility requirements will be asked to participate in further screening and will sign a study-specific Ethics Committee (EC) approved study informed consent form.

A “Screening Log” is provided to the investigational sites to maintain a cumulative log of all screened subjects. For subjects who are ineligible for participation in the clinical investigation or choose not to participate, a reason supporting the disqualification of the subject shall be entered on the Screening Log. Sites are not required to enter any data into the EDC system for screen failures.

9.2 SCHEDULE OF ASSESSMENTS

The schedule of study assessments through the 60-month clinical follow-up is shown in **Table 3**. Details of selected assessments are provided below.

Table 3: Schedule of Assessments

Assessment	Baseline and Pre-operative	Surgery Date	7-Day or Discharge	30 Days (+ 20/- 0 d)	6 Months (+/- 30 d)	12 Months (+/- 30 d)	18 Months (+/- 30 d)	24 Months (+/- 60 d)	36 Months (+/- 60 d)	48 Months (+/- 60 d)	60 Months (+/- 60 d)
Medical History	X										
3D Transoesophageal Echocardiogram (TOE) ¹	X	X									
Transthoracic Echocardiogram (TTE)	X		X	X	X	X	X	X	X	X	X
Patient Eligibility Assessment by Patient Eligibility Committee Report ²		X									
NYHA Heart Failure Class	X			X	X	X	X	X	X	X	X
Physical exam	X		X	X	X	X	X	X	X	X	X
STS score risk assessment	X										
EURO score risk assessment	X										
Study Consent Signed	X										
Laboratory Assessments ³	X										
Electrocardiogram (ECG)	X			X	X	X	X	X	X	X	X
6 Minute Walk Test	X				X	X					
SF-36 Quality of Life Assessment	X				X	X					
KCCQ Quality of Life Assessment	X				X	X					
Pregnancy test (if applicable)	X										
Medications & Dosage ⁴	X	X	X	X	X	X	X	X	X	X	X
Adverse Events		X	X	X	X	X	X	X	X	X	X

¹The 3D TOE previously-completed as part of the standard of care to assess the patient's suitability for treatment with the HARPOON System will be collected as part of historical data in the study. This assessment does not need to be repeated for study purposes.

²As part of clinical assessment for suitability for treatment with the HARPOON System, the patient will have already undergone an assessment of TOE by a Patient Eligibility Committee (PEC) as part of the standard-of-care. The report from this assessment will be collected as part of historical data in the study.

³Laboratory assessments performed as part of the standard of care will be recorded including (if performed) WBC count, haemoglobin, haematocrit, platelet count, creatinine, INR, total albumin, total bilirubin, BNP, and NTproBNP.

⁴All cardiac medications will be recorded within the study. Changes in medications will be documented in the medication log within the EDC system.

9.3 SCREENING EVALUATIONS AND PATIENT ELIGIBILITY COMMITTEE

All screening testing and assessment to determine if a patient is suitable for treatment with the HARPOON System is conducted within the standard-of care at the hospital outside of the study. This assessment includes the review of the patient's 3D TOE by a Patient Eligibility Committee (PEC) who will independently assess the eligibility of the patient for general treatment with the device.

Only once a patient is confirmed to be eligible (Pass) for treatment with the HARPOON System, is the patient approached for inclusion in the post-market study. Once consented and enrolled, the results of the previously-conducted HARPOON System suitability screening will be recorded as historical data.

9.4 BASELINE/PRE-PROCEDURE EVALUATIONS

Once the subject has signed a study informed consent, data from the following assessments which would have already been conducted as part of the standard of care, will be recorded:

- Routine laboratory assessment (recording any of the following that are done as part of the standard of care: WBC count; haemoglobin haematocrit, platelet count, creatinine, INR, total albumin, total bilirubin, BNP, NTproBNP)
- Routine electrocardiogram (ECG)
- Routine physical examination
- Assessment of NYHA Heart Failure Class
- Transthoracic echocardiogram (TTE)
- 3D Transoesophageal echocardiogram (TOE)
- Patient Eligibility Committee report of the TOE
- Assessment of Medical History

The following baseline assessments will be conducted as part of the study following informed consent.

- Assessment of STS score risk
- Assessment of EURO score risk
- 6 Minute Walk Test
- Quality of Life Assessment - SF-36
- Quality of Life Assessment - KCCQ
- Assessment of cardiac medications
- Pregnancy test (if applicable)

9.5 TREATMENT/PROCEDURE ASSESSMENTS

9.5.1 PROCEDURE OVERVIEW:

The HARPOON System procedure will be conducted in accordance to the HARPOON System CE-Mark Instructions for Use.

The study investigator will be trained in device use through didactic, practicum training, and proctoring. Complete details on the preparation and use of the HARPOON System can be found in the device's Instructions for Use.

9.5.2 CONVERSION TO MITRAL VALVE SURGERY

If in the judgment of the operating surgeon, adequate MR reduction has not been achieved, or if for any other clinical reason, conversion to standard-of-care mitral valve surgery shall be performed. Subjects who undergo a conversion to standard-of-care mitral valve surgery shall continue safety assessments (all tests identified in this protocol at each follow-up visit) through 30 days or until resolution of any adverse events related to the procedure, and then exited from the study.

9.5.3 PRIMARY FOLLOW-UP ASSESSMENTS

Post-procedure management: Standard hospital protocols for the management of subjects after mitral valve surgery shall be followed.

7-Day/Discharge assessment: All subjects shall be discharged from the hospital at the discretion of the attending cardiac surgeon. Prior to discharge, all subjects shall undergo a comprehensive pre-discharge TTE as well as a physical exam on either day 7 or at the time of discharge, whichever occurs first.

Primary subject follow-up: Subjects shall be seen at 30 days (+20/-0 days) after the HARPOON System procedure. A TTE and specific clinical assessments, in accordance with the Schedule of Assessments, shall be performed at that time.

Additional clinical and TTE follow-up shall occur for all active subjects in accordance with the Schedule of Assessments at the following intervals:

- 6-months (+/- 30 days)
- 12-months (+/- 30 days)
- 18-months (+/- 30 days)
- 24-months (+/- 60 days)
- 36-months (+/- 60 days)
- 48-months (+/- 60 days)
- 60 months (+/- 60 days)

9.6 MISSED FOLLOW-UP

The Investigator(s) will make every attempt to follow the subjects. All subjects will be encouraged by the Investigator(s) to report any address or telephone number changes to the study site personnel. Subjects should be informed of the importance of returning for scheduled follow-up visits even if they are not having any medical issues.

If a subject cannot be reached for a follow-up visit, or misses a scheduled visit, and is not willing to go to a local hospital/clinic for protocol-required assessments, the visit will be recorded as a missed visit on the date of last attempted contact. The procedure for attempts at contact should be two phone calls made and recorded in the study medical record. Subjects who miss a visit will not be considered

withdrawn. Subjects who miss two (2) sequential follow-up visits may be considered lost to follow-up at the second missed visit, and exited from the study.

9.7 STUDY EXIT CRITERIA AND PROCEDURES

The reason for study exit will be documented on the appropriate case report forms and in the medical records for each subject who exits the study.

Subjects may exit the study for any of the following reasons:

- Screen Failure
- Device Attempted but Not Implanted
 - Enrolled subjects for whom the implant procedure was prematurely aborted (e.g., entered operating room and anesthesia induced, but study procedure not attempted) or the HARPOON procedure was attempted but device not implanted, will be followed for 30 days or until resolution of any adverse events related to the implant procedure, and then exited from the study.
- Device Reintervention or Explant
 - Subjects who have a surgical reintervention where the device is explanted will be followed for 30 days post-reintervention or until resolution of any adverse events related to the procedure, and then exited from the study.
- Completion per Protocol
- Withdrawal
 - Subject Withdrawal: The subject may voluntarily withdraw from the clinical study at any time, without penalty or loss of benefits to which they are otherwise entitled.
 - Physician Withdrawal: The Investigator also has the right to withdraw a subject if s/he feels it is in the best interest of the subject.
 - Sponsor Withdrawal: The Sponsor may prematurely terminate the study. Circumstances under which the Sponsor can suspend or stop this trial include, but are not limited to, low study enrolment or new information regarding safety or efficacy.
- Death
- Lost to Follow-up
 - If a subject cannot be reached for a follow-up visit, the Investigator will document the contact efforts made to the subject and/or effort to obtain hospital records in the appropriate electronic case report form.

For subjects who are lost-to-follow-up or withdraw early, Edwards may request the site to search

death registries as available or applicable per GDPR requirements and may request the site to obtain the death certificate, if applicable.

In all cases of withdrawal (as described above), withdrawn subjects will not undergo further study follow-up procedures after the time of study exit. A study subject who has been withdrawn from the study will not be replaced.

9.8 DEATH AND SURGICAL VALVE INTERVENTION

9.8.1 DEATH

In the event of subject death, every effort should be made to obtain a copy of a death summary/death certificate. Information on the cause of death will be determined by the investigator(s) and reported in the study EDC system.

9.8.2 SURGICAL VALVE INTERVENTION

In the event of explant/subject surgical valve intervention, every effort should be made to obtain a copy of the procedure notes as well as any accompanying imaging data (CT, echo). Information on the cause of explant/surgical intervention will be determined by the investigator(s) and reported in the study EDC system. Subjects who have a surgical reintervention or whose device is explanted will be followed for 30 days or until resolution of any adverse events related to the procedure, and then exited from the study. Effort should also be made to return any explanted study devices to the Sponsor for analysis by the Edwards Complaint Handling team. Return kits for explanted devices will be provided, upon request, by the Edwards Surgical Complaint Handling Department.

10.0 ENDPOINT ANALYSIS AND STATISTICAL METHODS

10.1 ANALYSIS POPULATION

The analysis population is the 250 subjects who were implanted and entered the HARPOON System procedure, regardless of procedure outcome. The analysis population excludes any subjects who signed the study consent (were enrolled) but were exited from the study prior to the procedure.

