4.0 PROTOCOL SYNOPSIS

Title:	ASsessment of the safety and performance of the HARPOON™ Beating Heart Mitral Valve Repair System; a multicenter post-market study (ASCEND)
Protocol Number:	2018-22
Sponsor	HARPOON Medical, an indirect wholly-owned subsidiary of Edwards Lifesciences Corporation
Design:	A single arm, prospective, multicentre, non-randomised and open-label post-market study
Device:	HARPOON™ Beating Heart Mitral Valve Repair System (MVRS)
Population:	Patients with severe degenerative mitral regurgitation as a result of mid-segment posterior leaflet prolapse undergoing treatment with HARPOON™ Beating Heart Mitral Valve Repair System
Enrolment:	250 implanted subjects in up to 25 centers in Europe
Duration:	Initial enrolment: Q4 2019 Last enrolment: Q4 2021 Last follow-up visit: Q1 2027
Follow-up:	Follow-up at 7 days or discharge from hospital post-index procedure (whichever occurs first), at 30 days, and at 6, 12, 18, 24, 36, 48, and 60 months post-treatment
Objectives:	To evaluate the long-term safety and performance of the HARPOON™ MVRS for use in patients presenting with severe degenerative mitral regurgitation due to posterior leaflet prolapse in the post-market phase.
Endpoints:	Primary Safety Endpoint: 
➤ Freedom from all-cause mortality, disabling stroke and life-threatening bleeding at 30 days post-implant. Primary Performance Endpoint: 
➤ Procedure success at 30 days post-treatment, as measured by: Technical success with reduction of MR to less than or equal to mild and the absence of major device or procedure-related SAEs.
Other Planned Analyses:	
➤ Technical success defined as survival and exit from the operating room (OR) with successful implantation of 3 or more expanded polytetrafluoroethylene (ePTFE) chords.➤ Freedom from major device or procedure-related serious adverse event (SAE) at 30 days, 1 year and 2 years post-implant➤ Quality of Life (change from baseline to 1 and 6 months)

- 6-minute walk test (change from baseline to 1 and 6 months)
- Freedom from ePTFE chord rupture as reported by echo core lab at 1 year and 2 years post-implant
- Freedom from reoperation or re-intervention due to ePTFE chord rupture at 1 year and 2 years post-implant
- Functional improvement from baseline NYHA Functional Classification at 1 year and 2 years post-implant

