 - Structural or Functional failure of the HARPOON device, introducer or artificial chords (ePTFE) requiring an intervention.
 - Conversion to the Open Mitral Valve Surgery secondary to mitral valve apparatus damage or dysfunction, requiring surgical valve repair or replacement, or Secondary to procedural complications (such as cardiac perforation, removal of an embolized artificial chords, injury to Aortic valve and so on)
 - Device malpositioning (Artificial chords malpositioning) requiring intervention. Permanent deployment of **artificial chord(s)** in a location other than intended or movement of the artificial chords during or post deployment which requires an intervention.
 - Artificial Chord detachment (used with HARPOON device) which requires an intervention
 - Device fracture: a break, tear, perforation, or other structural defect in the artificial chords (housing, leaflet, and so on) resulting in device failure, resulting in recurrent MR symptoms, or requiring reintervention.
 - Damage to the native mitral valve apparatus (damage to native chordae tendinae, Leaflets, Papillary muscles or Mitral annulus) requiring an intervention or conversion to Open Mitral Valve Surgery.
 - Symptomatic or requiring intervention Device Thrombosis (any thrombus attached or near the artificial HARPOON implanted chords)
 - Interaction with non-mitral valve intracardiac structures which requires intervention and
 - Endocarditis (as diagnosed by modified Duke endocarditis criteria or evidence of abscess, pus, or vegetation confirmed as secondary to infection

by histological or bacteriological studies during an operation or autopsy) which required a surgical intervention.

- Hemolysis (a presence of a leaflet perforation on transesophageal or transthoracic echocardiography plus anemia requiring transfusion plus increased haptoglobin and/or LDH levels; which lead to a surgical intervention.
- Other major device or procedure related SAEs

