10.2 SAMPLE SIZE RATIONALE

Edwards has established a minimum sample size of 250 participants for this study. The rationale for this sample size can be viewed from two different perspectives: precision of estimation and statistical monitoring for product failure.

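### Section 10.1 leaves open whether subjects whose HARPOON procedure was begun but who received no implant are in the primary denominators; read literally, it drops them and overstates procedure success

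*Combined protocol and SAP*

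**What the plan says.** Section 10.1 gives the analysis population in two sentences. The first is "The analysis population is the 250 subjects who were implanted and entered the HARPOON System procedure, regardless of procedure outcome". The second is "The analysis population excludes any subjects who signed the study consent (were enrolled) but were exited from the study prior to the procedure". The word *implanted* is not defined there.

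The number 250 is tied to implants elsewhere. The synopsis gives enrolment as "250 implanted subjects in up to 25 centers in Europe", and Section 7.4 says that 250 "subjects will be implanted at up to twenty-five (25) centers in Europe". Section 10.2 is looser: "Edwards has established a minimum sample size of 250 participants for this study".

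The protocol expects some procedures to end without an implant. For conversions to standard mitral surgery, Section 9.5.2 has this wording: "shall continue safety assessments (all tests identified in this protocol at each follow-up visit) through 30 days". It offers resolution of procedure-linked events as the alternative end of follow-up, after which the subject leaves the study. For attempted procedures that leave no device in place, Section 9.7 has this wording: "the HARPOON procedure was attempted but device not implanted, will be followed for 30 days or until resolution of any adverse events". Those subjects leave the study afterwards as well. Neither section says whether these subjects count in a primary denominator.

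Technical success (Section 7.3.3) requires the subject to leave the operating room alive with at least three chords implanted. It is a component of procedure success, the primary performance endpoint (Section 7.3.2). The primary safety endpoint (Section 7.3.1) is timed from implant.

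**The concern.** The first sentence of Section 10.1 joins two conditions, implanted and entered the procedure, and attaches the implanted count of 250. Applied literally, it removes subjects in whom the procedure was started and abandoned or converted. The phrase about procedure outcome can then be read as applying only within the implanted group.

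Every subject removed in this way is a certain failure on the primary performance endpoint, so the headline success rate would be conditional on having got the device in. Failures among implanted subjects (fewer than three chords, MR above mild, a major related SAE) count on either reading.

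If the wording stays as it is, the denominator may be chosen after the data are known.

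**Working it through.** **The plan's own figures.** Section 6.3.5 reports procedural success of 11/13 = 84.6% (EFS) and 46/52 = 88.5% (CE Mark). Both reproduce. The precision goal in Section 10.2.1 (5 points or better at n = 250 for rates of 2% to 17%) also holds with the normal-approximation half-width: 1.96 × √(0.17 × 0.83 / 250) = 4.7 points at 17%, and 1.7 points at 2%.

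**Can Section 10.1 be both inclusive and 250?** Let *q* be the share of procedures begun that end with no implant. With 250 implanted, procedures begun number 250 / (1 − *q*). That equals 250 only if *q* = 0, and Sections 9.5.2 and 9.7 provide for *q* above zero. So the inclusive reading does not fit the figure of 250 as an implanted count, and the literal reading sits badly with the sole stated exclusion.

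**Direction for procedure success.** All successes lie among implanted subjects. If their success rate is *s*, the literal reading reports *s* and the inclusive reading reports *s* × (1 − *q*). The gap is *s* × *q*, which is never negative.

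**Illustrative size.** From Section 6.3.3, 65 were enrolled and 13 + 49 = 62 implanted. Of the three who left without a device, one was aborted before the HARPOON procedure (left out here) and two were converted, so 64 procedures were begun. All three were in CE Mark (52 − 49 = 3), which gives 51 begun in that trial. Successes are 11 + 46 = 57 pooled.

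| | Implanted only | Procedure begun | Gap (before rounding) |
|---|---|---|---|
| Pooled | 57/62 = 91.9% | 57/64 = 89.1% | 2.9 points |
| CE Mark | 46/49 = 93.9% | 46/51 = 90.2% | 3.7 points |

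The share 2/64 = 3.1% has an exact (Clopper-Pearson) 95% interval of 0.38% to 10.84%. At *s* = 0.919:

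- lower end: 0.919 × 0.0038 = 0.35 points
- upper end: 0.919 × 0.1084 = 10.0 points

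For scale, the 95% half-width at 91.9% with n = 250 is 1.96 × √(0.919 × 0.081 / 250) = 3.4 points.

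**Projected to 250 implants.** 250 / (1 − 2/64) = 258 procedures begun, so 8 failures would go uncounted. With an assumed 225 successes, 225/250 = 90.0% against 225/258 = 87.2%, a gap of 2.8 points.

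**Safety endpoint.** Assume 5/250 = 2.0% with an event among implanted subjects (the low end of the range in Section 10.2.1) and 8 non-implanted subjects. Including those 8 gives:

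- no event among them: 5/258 = 1.94%
- one event: 6/258 = 2.33%
- two events: 7/258 = 2.71%

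The shift can go either way, and the documents give no event rate for such subjects.

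**The case against.** The best defence is that the protocol, read as a whole, already means everyone who entered the procedure. Section 10.1 disregards procedure outcome, and its only exclusion is exit beforehand; had begun-but-not-implanted subjects also been excluded, that sentence would omit the most obvious group. These subjects are followed after the procedure. Section 10.2 calls 250 a minimum. Section 7.3.4 lists among major SAEs "Conversion to the Open Mitral Valve Surgery secondary to mitral valve apparatus damage or dysfunction, requiring surgical valve repair or replacement", so some conversions are treated as endpoint failures. Section 6.3.5 reported earlier procedural success on the enrolled cohort, which included all three subjects without a device.

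Most of this stands, and it makes the inclusive reading at least as well supported. It does not close the matter. *Implanted* and 250 remain in the definition, a minimum does not say who is counted, and precedent is mixed because Table 1 in Section 6.3.4 uses the implanted cohort. Section 10.6.4 points to a pre-specified SAP, but nothing in the combined document settles the denominator.

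Three further objections also stand:

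- The size rests on two subjects. The earlier success definitions differ from this study's (one or more chords; MR up to moderate in CE Mark), and screening and procedure were later revised (Section 6.3.6.1).
- Correcting the safety denominator is not only a matter of Section 10.1. Sections 9.5.2 and 9.7 allow follow-up to end at 30 days or on resolution of events, so 30-day status is not assured. Classifying a stroke as disabling also needs a modified Rankin score 90 days after onset (Section 7.3.4).
- The primary endpoints are summarised descriptively (Section 10.5), so no pass/fail decision turns on this.

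A reader might infer that the plan does exclude failed procedures and will report an inflated success rate. The documents do not support that: the text permits the exclusion without clearly requiring it. Nor do they support a claim that the safety result would look better than it is, since the direction there is unknown.

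**Conclusion.** The wording of Section 10.1 is ambiguous on a point that sets the denominator of both primary endpoints. If the literal implanted-only reading is applied, procedure success is overstated whenever at least one begun procedure ends without an implant and at least one implanted subject succeeds; this follows from the endpoint definition. Under the inclusive reading the overstatement is zero.

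The size under the literal reading is about 3 points if the earlier non-implant share of 2/64 carries over and success among implanted subjects is near 92%. The range is roughly 0.35 to 10 points over the exact interval for that share. At the central value the shift is close to the sampling half-width of 3.4 points. These figures illustrate scale and are not a forecast for this study.

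The ambiguity does not undermine the sample size. 250 subjects meet the stated precision goal, and the inclusive reading adds to that number.

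**What to change.** In Section 10.1, delete *implanted* and the figure of 250 from the definition. State that the primary analysis population for both primary endpoints is every consented subject in whom the HARPOON procedure was begun, whether or not chords were implanted, and that non-implanted and converted subjects count as procedure failures. Say what counts as begun, since Section 9.7 also describes cases stopped after anaesthesia with the study procedure not attempted. Keep 250 as the implant target in the synopsis and Section 7.4. Report the implanted subset as a secondary analysis and for the durability endpoints. Carry the same definition into the SAP.

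In the same edit, count the 30-day safety window from the index procedure for non-implanted subjects, who have no implant date. Reconcile the follow-up wording of Sections 9.5.2 and 9.7 so that 30-day status is recorded for them.

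The cost is a text amendment, a small change to the follow-up wording, and possibly a slightly less favourable headline success rate. Performance scoring for these subjects needs only their status on leaving the operating room.
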